3.10.2 Screening AKI and Screening eGFR

Screening (pre-dose) AKI will be determined by comparing screening (pre-dose) creatinine to the algorithmic determination of reference as described in Exhibit 1 based on the rules summarized in Exhibit 2.

The screening creatinine is necessary to establish baseline eGFR. However, according to the Clinical Protocol, the AKI stage used to determine eligibility into the study may be determined through urine outcome criteria. If there is any discrepancy between the algorithm and the assignment by the site as to reference creatinine then this will generate a medical review which may result in a modified baseline AKI stage different from the algorithmic determination. However, in all cases, the algorithmic determination will be used when determining eGFR. All such cases will be documented in the clinical study report. Sensitivity analyses will be conducted as needed to evaluate the impact of any modifications from the algorithmic determination in Screening AKI stage.

Exhibit 2. Algorithmic Determination of Screening (pre dose) AKI Stage	
Stage	Serum Creatinine
0	<1.5 times reference
1	1.5 to <2.0 times reference
2	≥2 to 3 times reference
3	≥ 3 times reference OR Increase in serum creatinine to ≥4 mg/dL OR Initiation of renal replacement therapy
Reference may be either algorithmically determined or independently adjudicated depending on analysis.	

Screening eGFR will be determined using the following formula.

$$\text{Screening eGFR (mL/min/1.73 m}^2\text{)} = 175 \times (\text{Screening Cr})^{-1.154} \times (\text{Age})^{-0.203} \times (0.742 \text{ if female}) \times (1.212 \text{ if African American}).$$

3.10.3 Day 28 eGFR

Day 28 eGFR will be determined by converting Day 28 creatinine to Day 28 eGFR using the following formula:

$$\text{Day 28 eGFR (mL/min/1.73 m}^2\text{)} = 175 \times (\text{Cr Day 28})^{-1.154} \times (\text{Age})^{-0.203} \times (0.742 \text{ if female}) \times (1.212 \text{ if African American}).$$

Percentage loss in eGFR at Day 28 will be determined using the following formula.

$$\text{Percentage loss in eGFR at Day 28} = 100\% \text{ times } [\text{Screening eGFR} - (\text{Day 28 eGFR}) / \text{Screening eGFR}]. \text{ If percentage loss } \geq 37\% \text{ then patient fails key secondary endpoint.}$$

3.10.4 Day 14 eGFR

Day 14 eGFR will be determined by converting Day 14 creatinine to Day 14 eGFR using the following formula:

$$\text{Day 14 eGFR (mL/min/1.73 m}^2\text{)} = 175 \times (\text{Cr Day 14})^{-1.154} \times (\text{Age})^{-0.203} \times (0.742 \text{ if female}) \times (1.212 \text{ if African American}).$$

Percentage loss in eGFR at Day 14 will be determined using the following formula.

Percentage loss in eGFR at Day 14 = 100% times [Screening eGFR - (Day 14 eGFR) / Screening eGFR]. If percentage loss $\geq 37\%$ then patient fails the Day 14 endpoint.

3.10.5 Day 90 eGFR

Day 90 eGFR will be determined by converting Day 90 creatinine to Day 90 eGFR using the following formula:

Day 90 eGFR (mL/min/1.73 m²) = $175 \times (\text{Cr Day 14})^{-1.154} \times (\text{Age})^{-0.203} \times (0.742 \text{ if female}) \times (1.212 \text{ if African American})$.

Percentage loss in eGFR at Day 90 will be determined using the following formula:

Percentage loss in eGFR at Day 90 = 100% times [Screening eGFR - (Day 90 eGFR) / Screening eGFR]. If percentage loss $\geq 37\%$ then patient fails the Day 90 endpoint.

3.10.6 Additional Processing Details

Based on experience gained through processing of AKI endpoints in the recently completed ATB-202 study, the following data processing convention will be employed.

- To account for renal replacement therapy (RRT), the exact dates on which the patient is on dialysis will be determined and compared to the exact date on which the labs were drawn for the creatinine sample. If the sample was drawn within 2 days from RRT start then it was excluded from all analyses.
- If the reference creatinine is greater than 1.4, then all available creatinine values obtained on Day 10 and after, including unscheduled visits, will be evaluated. If the maximum is 1.5x the minimum, then the reference creatinine is replaced by the MDRD.
- LOCF will be used for missing Day 14 creatinine starting from Day 10.
- LOCF will be used for missing Day 28 creatinine starting from Day 7.

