- Assess lesion status if NSTI (healing/progression/significant change in appearance) if accessible for visible assessment at time of debridement or routine dressing change
- Record Survival

Visit 8 (Day 21 [±1 day])

- Collection of AEs/SAEs, including secondary infections
- Collect data on additional amputations if NSTI
- Collect data on acute RRT
- Record additional relevant procedures related to the kidney (e.g., renal biopsy)
- Record any imaging that evaluates the kidney
- Concomitant medications
- Critical care parameters (dates and times of assisted ventilation, vasopressor use, ICU /hospital stay)
- Record any hospital re-admissions (if previously discharged for original sepsis-related hospitalization)
- Vital Signs (to be taken during the morning tests if still hospitalized)
- Serum creatinine
- Record Survival

Visit 9 (Day 29 [+3 days])

- Weight
- Collection of AEs/SAEs, including secondary infections

- Collect data on acute RRT
- Record additional relevant procedures related to the kidney (e.g., renal biopsy)
- Record any imaging that evaluates the kidney
- Collect data on additional amputations if NSTI
- Concomitant medications
- Critical care parameters (dates and times of assisted ventilation, vasopressor use, ICU /hospital stay)
- Vital signs (to be taken during the morning tests if still hospitalized)
- Serum creatinine and albumin
- CBC with differential and platelet count
- Standard CRP
- Spot urine for albumin to creatinine ratio
- Collect blood for serum for storage (immunogenicity testing)
- Record any hospital re-admissions (if previously discharged for original sepsis-related hospitalization)
- Record Survival

All efforts should be made to collect these data, especially laboratory data, with Day 28 being the primary endpoint, but in case parameters cannot be collected, phone follow-up will be performed, and information that could be collected over the phone will apply.

Visit 10 (3 to 21 Days after Visit 9)

- Serum creatinine

Visit 11 (Day 90 [+5 days])

The 3-month visit is a follow-up visit to assess the long-term health condition of the patients including assessment of

- Serum creatinine
- Spot urine for albumin to creatinine ratio
- Serum for storage (immunogenicity test)
- Record survival
- Record any hospital readmission(s) within 30 days of discharge from original sepsis-related hospitalization.

Follow-up of Patients

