9.2.8 Acute Kidney Injury

During screening, it will be recorded whether the patient presented with Stage 2 or 3 AKI, or developed Stage 2 or 3 AKI within 48 hours after the suspected or confirmed diagnosis of abdominal infection, or surgical confirmation of NSTI. If a reference (baseline) serum creatinine value(s) is/are available from the past 12 months, the reference serum creatinine value(s) and date(s) obtained will be entered. If the subject does not have a reference serum creatinine value, it will be noted if the serum creatinine is ≥ 2.0 fold normal for age, race, and gender, and the length of the largest kidney by CT or renal ultrasound.

The stage of AKI (Stage 2 or 3) and how AKI was diagnosed (serum creatinine or urine output or both) will be recorded. The screening creatinine value prior to study drug administration as well as additional creatinine values from presentation or around (before) time of diagnosis of abdominal infection or NSTI should be entered. Urine output should be computed from presentation or around (before) time of diagnosis of abdominal infection or NSTI after accurate urine output is recorded. After study drug administration, urine output is collected while subject is in the ICU or step-down unit (or equivalent) with or without a Foley catheter in place through Day 7.

If receiving RRT, then the type of RRT and net fluid removed per RRT session will be collected through Day 28. Additional renal imaging or renal procedures (e.g., renal biopsy) performed as part of SoC through Day 28 will be entered in the eCRF.

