9.2.11.6 Renal Replacement Therapy Guidelines

Renal replacement therapy guidelines are provided only to guide the clinicians. Initiation and stopping of renal replacement therapy can occur based on the clinicians/institution's protocols/judgement. Continuous and intermittent-non-continuous modalities such as intermittent hemodialysis (IHD) are allowed after administration of study drug. RRT may be started prior to study drug administration as long as the patient is off the treatment from time of study drug administration and up to at least one hour post study drug administration.

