4.1 Primary Effectiveness Endpoint

The primary effectiveness endpoint is *freedom from durable loss of renal function at Day 28*. The primary effectiveness endpoint requires:

- (i) Alive at Day 28,
- (ii) Free of dialysis at Day 28, and
- (iii) Less than a 37% loss of estimated Glomerular Filtration Rate (eGFR; measured with the Modification of Diet in Renal Disease (MDRD) formula from the patient's reference eGFR) at Day 28.

Reference creatinine values, baseline AKI stage and percentage loss of eGFR at 28 will be determined through algorithmic determination (see details above). Percentage loss of eGFR determined algorithmically will be based on a comparison of eGFR at screening compared to an algorithmically determined reference creatinine value.

Note: The Clinical Protocol allows subjects to qualify for enrollment in terms of AKI stage through urine outcome.

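### The SAP drops creatinines only near the start of RRT and does not define dialysis-free status at Day 28, so dialysis-lowered values and patients between sessions are not reliably kept out of the success count

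*SAP*

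**What the plan says.** SAP 3.10.6 sets the RRT convention. It says that "the exact dates on which the patient is on dialysis will be determined and compared" with the date of the creatinine draw, and then gives one exclusion: "If the sample was drawn within 2 days from RRT start then it was excluded from all analyses". It has no rule for a sample taken later in a course or after the last session.

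The same section says: "LOCF will be used for missing Day 28 creatinine starting from Day 7". It also replaces a reference creatinine above 1.4 by an MDRD-derived value if, among all creatinines from Day 10 on, the maximum is 1.5 times the minimum. SAP 3.10.7 adds a sensitivity analysis that uses the mean of the Day 14 to Day 28 creatinines, or the last of them if they are unstable.

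SAP 4.1 lists the dialysis component of the primary endpoint as "Free of dialysis at Day 28, and". SAP 2.1.1 and 8.1 and protocol 10.1 and 12.1 use equivalent wording. None gives a window.

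Protocol 9.2.11.6 says: "Continuous and intermittent-non-continuous modalities such as intermittent hemodialysis (IHD) are allowed after administration of study drug". Protocol 9.2.8 says: "If receiving RRT, then the type of RRT and net fluid removed per RRT session will be collected through Day 28". The scheduled creatinine that serves Day 28 is drawn at Visit 9, on Day 29 with a window of plus 3 days (protocol 7.3).

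**The concern.** Dialysis removes creatinine, so a value drawn on RRT or shortly after it overstates kidney function. The SAP recognises this by having an exclusion at all, but ties it to the wrong end of the exposure: contamination lasts throughout RRT and for some time afterwards, not only around its start.

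The dialysis component should catch a patient who is still dependent, whatever the creatinine shows. Intermittent RRT is allowed, so a dependent patient can have days without a session, and the SAP does not say how that patient is classified. Whoever programs the endpoint must choose a reading.

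At stake is what the primary endpoint means: a patient still on dialysis has not been shown to be free of durable loss of renal function. If such patients are counted as successes unequally across arms, the treatment difference is also distorted.

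**Working it through.** **1. What the exclusion does under each reading**

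| Meaning of RRT start | Continuous RRT | Intermittent RRT |
|---|---|---|
| Start of a course | Samples from the rest of the run, and just after it, are kept | The same |
| Start of each session | One long session, so the same as above | Most samples in a three-a-week patient are dropped; LOCF from Day 7 fills Day 28 |

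Kept values can reach three places: LOCF to Day 28; the check from Day 10 on, where a dialysis-lowered minimum can trigger replacement of the reference; and the Day 14 to 28 sensitivity mean.

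**2. Can the eGFR component act as a backstop?**

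MDRD eGFR varies as creatinine to the power −1.154. A 37% loss therefore corresponds to a creatinine ratio of (1/0.63)^(1/1.154) = 1.49.

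- Against the reference, a patient at k times reference passes if dialysis has lowered creatinine by more than 1 − 1.49/k: 25% at k = 2, 50% at k = 3, 63% at k = 4.
- SAP 3.10.3 uses screening eGFR as comparator. With its bracket read as (screening − Day 28)/screening, a patient screened at 2, 3 or 4 times reference passes up to 2.98, 4.48 or 5.97 times reference. That mismatch with the endpoint wording is a separate issue. Here it shows that the eGFR component cannot be relied on to catch dialysis patients.

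**3. The plan's own power**

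With n = 60 per arm and the pooled chi-square approximation:

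power = Φ{[Δ − z·√(2p̄(1−p̄)/n)] / √[pC(1−pC)/n + pT(1−pT)/n]}

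For 50% vs 75%, Δ = 0.25, p̄ = 0.625, and the two standard errors are 0.0884 and 0.0854.

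- One-sided 0.05: (0.25 − 1.645 × 0.0884)/0.0854 = 1.225, giving 89.0%. SAP 2.1.2 states 89%.
- One-sided 0.025: (0.25 − 1.960 × 0.0884)/0.0854 = 0.899, giving 81.6%. Protocol 12.5.2 states 81.6%.

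**4. Illustration of the dialysis component**

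The documents give neither a session schedule nor the share of patients dependent at Day 28. Assume three sessions a week, so 4/7 = 57% of days have no session, and assume that patients on such days are read as dialysis-free. If 10% of an arm (6 of 60) is dependent, 6 × 4/7 = 3.4 patients are misread. Let g be the share of misread patients who also pass on creatinine. Each arm's apparent success rate rises by dependence × 4/7 × g.

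Worst case, 5% active vs 15% placebo, g = 1: pC = 0.50 + 0.15 × 4/7 = 0.586 and pT = 0.75 + 0.05 × 4/7 = 0.779, so Δ = 0.193.

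| Dependence, active / placebo | g | Δ (points) | Power, one-sided 0.025 | Power, one-sided 0.05 |
|---|---|---|---|---|
| None misread | – | 25.0 | 81.6% | 89.0% |
| 5% / 15% | 1 | 19.3 | 62.4% | 73.8% |
| 5% / 15% | 0.5 | 22.1 | 72.8% | 82.4% |
| 5% / 15% | 0.1 | 24.4 | 79.9% | 87.8% |
| 10% / 10% | 1 | 25.0 | 84.6% | 91.1% |
| 15% / 5% | 1 | 30.7 | 96.0% | 98.1% |

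The direction depends on which arm has more dependent patients.

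**The case against.** A reader might infer that dialysis status is judged on a single calendar day, so that the plan counts dependent patients as successes. The documents do not say that. Dialysis-free at Day 28 can equally mean no ongoing RRT course, and then the dependent patient fails. A patient on continuous RRT on Day 28 fails under any reading. What stands is that the term is undefined.

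A carried-forward on-RRT value needs particular circumstances. For a patient on RRT from Day 3 to Day 9, the Day 7 value reaches Day 28 only if the Day 14, 21 and 29 creatinines and any Day 10 value are all missing, and that patient is not dialysis-dependent at Day 28. LOCF cannot reach back before Day 7. Under the per-session reading, the rule does remove most dialysis-lowered values in intermittent RRT. All of this limits how often the problem arises. It does not mend the rule for continuous RRT or for the course reading.

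The protocol also offers possible safeguards: blinded adjudication with RRT dates supplied (10.1, 10.4) and a confirmatory creatinine 3 to 21 days after Visit 9 (12.11.2). The SAP does not expressly remove them. However, SAP 4.1 determines percentage eGFR loss by algorithm, SAP section 1 gives the SAP precedence where the two documents differ, and no SAP endpoint rule uses either safeguard. They do not close the gap as written.

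**Conclusion.** The point holds as a defect in a stated rule and a gap in a definition. Read literally, SAP 3.10.6 keeps dialysis-lowered creatinines from most of any continuous run, and from most of any course if start means course start. SAP 4.1 does not say how a patient between sessions is classified, so a success in a dependent patient is not prevented.

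The size and direction are not known from the documents. A reader might take the fall from 81.6% to 62.4% (or from 89.0% to 73.8% at the SAP's one-sided 0.05) as the expected cost. It is not: it needs three sessions a week, the single-day reading, dependence of 5% vs 15%, and every misread patient passing on creatinine. If only 10% of them pass, power at 0.025 is 79.9%; with 10% dependence in both arms and all passing, it rises to 84.6%. Nothing here shows inflation of the type 1 error. The firmer argument is validity of the primary endpoint. Severity: should-fix, before unblinding.

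**What to change.** 1. **SAP 3.10.6.** Exclude any creatinine drawn on a day on RRT, or within 2 days after the end of any RRT session or course. Apply this to the endpoint, to LOCF, to the reference check from Day 10 on, and to the sensitivity analysis in 3.10.7.
2. **SAP 4.1** (and 2.1.1, 8.1). State that a patient with an ongoing RRT course at Day 28 fails the dialysis component whatever the creatinine. Define ongoing by a pre-specified look-back over the RRT dates collected through Day 28, for example 7 days, with a sensitivity analysis on its length. The 7 days is one choice among several; what matters is that a length is fixed.
3. **Anchor.** End the look-back at Day 28, not at the Visit 9 draw, because Visit 9 falls on Day 29 to 32 while protocol 9.2.8 promises per-session detail only through Day 28. Applying item 1 to the Visit 9 sample needs RRT dates up to the draw. Visit 9 does list acute RRT data, so confirm that these dates are captured.

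The cost is mainly SAP wording and programming. There will be slightly more LOCF, and a patient left with no eligible creatinine from Day 7 on needs a stated classification. A patient who stopped RRT within the look-back counts as a failure, which the sensitivity analysis on its length would show.

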12. STATISTICS

12.1 Primary Effectiveness Endpoint

The primary effectiveness endpoint for this study is:

- Rates of achieving the primary endpoint of freedom from durable loss of renal function (defined as alive, free of dialysis, and less than a 37% loss of eGFR; (measured with the MDRD formula from the patient's reference eGFR)) at Day 28.

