2.1 Primary Efficacy Analysis

2.1.1 Primary Superiority Hypothesis

The primary effectiveness endpoint is *freedom from durable loss of renal function at Day 28*. Success requires:

- Alive at Day 28,
- Free of dialysis at Day 28, and
- Less than a 37% loss of estimated Glomerular Filtration Rate (eGFR; measured with the Modification of Diet in Renal Disease (MDRD) formula from the patient's reference eGFR) at Day 28.

Reference creatinine values, baseline AKI stage and percentage loss of eGFR will be determined through algorithmic determination (see details below). Percentage loss of eGFR determined algorithmically will be based on a comparison of eGFR at screening compared to an algorithmically determined reference creatinine value.

The primary efficacy comparison involves testing the following one-sided superiority hypotheses: **H₀: $\pi_{0.50} - \pi_{\text{placebo}} \leq 0$ vs H_a: $\pi_{0.50} - \pi_{\text{placebo}} > 0$** ; where $\pi_{0.50}$ and π_{placebo} represent the true probability of freedom from durable loss of renal function at Day 28. Each probability represents the proportion of subjects on each arm expected to achieve complete recovery. These hypotheses will be tested using a one-sided type 1 error rate of $\alpha=0.05$. The null hypothesis will only be rejected if the investigational drug demonstrates superiority. An unadjusted chi-square test will be used to test this hypothesis.

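### The SAP gives three inconsistent bases for eGFR loss; once loss is taken from reference eGFR, creatinine from Day 10 on can replace a recorded reference above 1.4 and reverse some patients' results

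*SAP*

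**What the plan says.** **Endpoint definition.** SAP 2.1.1, 4.1 and 8.1 list three conditions for success: alive, free of dialysis, and less than a 37% loss from the patient's "reference eGFR) at Day 28". Protocol 12.1 agrees ("reference eGFR)) at Day 28").

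**Prose below the definition.** SAP 2.1.1 and 4.1 add that the loss rests on eGFR at screening "compared to an algorithmically determined reference creatinine value". That sentence contains no Day 28 value.

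**Printed formulas.** SAP 3.10.3 announces that "Percentage loss in eGFR at Day 28 will be determined using the following formula" and then uses Screening eGFR as the base. The other two visits follow the same pattern: "Percentage loss in eGFR at Day 14 = 100% times [Screening eGFR - (Day 14 eGFR) / Screening eGFR" and "Percentage loss in eGFR at Day 90 = 100% times [Screening eGFR - (Day 90 eGFR) / Screening eGFR", each closed by a square bracket.

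**Reference creatinine.** SAP 3.10.1, Exhibit 1, builds it from values up to 12 months old. If there are none, an MDRD back-calculation from an eGFR of 75 is used.

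**Replacement rule.** Under SAP 3.10.6, when the reference exceeds 1.4, "all available creatinine values obtained on Day 10 and after, including unscheduled visits, will be evaluated". Then: "If the maximum is 1.5x the minimum, then the reference creatinine is replaced by the MDRD". No unit, inequality or last day is given. SAP 3.8 schedules creatinine 3 to 21 days after the Day 29 visit and at 3 months, so those values count too.

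**The concern.** A reference value should describe the patient before the illness. Protocol 6.1 builds it only from values before admission, or from the admission value of a patient who was not acutely ill. SAP 3.10.6 lets creatinine measured after randomisation choose it instead. The result then depends on how creatinine moved after Day 10 as well as on renal function at Day 28, and a better Day 28 value can score worse.

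Protocol 12.11.2 plans the sample 3 to 21 days after Visit 9 to confirm creatinine, not to revise the reference. The SAP attributes the rule to experience in a recently completed study, but does not say why variation after Day 10 shows a pre-illness value to be wrong.

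The baseline conflict comes first. The replaced reference enters the loss only if loss is measured from reference eGFR. With the Screening eGFR formula it does not, and no claim about SAP 3.10.6 is made for that reading.

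**Working it through.** **Inputs**
- Limit: 37% loss (SAP 2.1.1, 4.1, 8.1).
- Forward equation: 175 × Cr^-1.154 × age^-0.203 × 0.742 if female × 1.212 if African American (SAP 3.10.2 to 3.10.5).
- Fallback reference: (75 / (186 × age^-0.203 × sex × race))^-0.887, race factor 1.21 (SAP 3.10.1 code).
- Trigger: reference above 1.4, read as mg/dL; maximum/minimum from Day 10 on, read as at least 1.5 (SAP 3.10.6).
- Patient profiles are my assumptions: alive, off dialysis, intermediate values lying between those stated.

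**1. The plan's own figure of 75.** Putting the coded fallback creatinine through the forward equation should return 75. For ages 18 to 85 and all four sex and race groups it returns 69.8 to 71.1, because 186, -0.887 and 1.21 are not the inverse of 175, -1.154 and 1.212 (1/1.154 = 0.867). The fallback creatinine is 4.8% to 6.4% too high.

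**2. The three bases**

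| Place | Comparison |
|---|---|
| SAP 2.1.1, 4.1, 8.1 bullets; Protocol 12.1 | Day 28 against reference |
| SAP 2.1.1 and 4.1 prose | Screening against reference |
| SAP 3.10.3, 3.10.4, 3.10.5 formulas | Day 28, 14 or 90 against Screening |

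Take a patient at exactly twice reference at screening, unchanged at Day 28. From reference, loss = 1 - 2^-1.154 = 55.1%: failure. From Screening, loss is 0%: success. (I read the formula as the difference divided by Screening eGFR; its inner bracket is misplaced.) The screening-against-reference comparison gives at least 55.1% for anyone at twice reference or more at screening, whatever the Day 28 result.

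**3. Failure limit from reference.** Loss = 1 - (Cr28/Ref)^-1.154. A 37% loss means Cr28/Ref = 0.63^(-1/1.154) = 1.492.

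**4. Reference after replacement, age 60**

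| Group | Fallback reference | Failure from (× 1.492) |
|---|---|---|
| Non-black man | 1.071 | 1.60 |
| Black man | 1.268 | 1.89 |
| Non-black woman | 0.822 | 1.23 |
| Black woman | 0.973 | 1.45 |

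**5. Non-black woman aged 60, recorded reference 1.5 (eGFR 35.4, so not excluded by the eGFR limit of 30 in Protocol 6.2)**

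| Case | Day 10 → Day 28 | Max/min | Reference used | Loss | Result |
|---|---|---|---|---|---|
| A | 2.4 → 1.5 | 1.60 | 0.822 | 50.1% | Failure |
| B | 2.2 → 2.2 | 1.00 | 1.5 | 35.7% | Success |
| C | 2.2 → 1.5 | 1.47 | 1.5 | 0% | Success |

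Day 28 eGFR is 35.4 in A and 22.8 in B. A and C have identical Day 28 function and differ only by 0.2 at Day 10.

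**6. Other profiles, non-black man aged 60**
- Reference 1.7, 2.6 falling to 1.7 (max/min 1.53): 41.3%, failure. Flat at 2.5: 35.9%, success.
- Reference 1.5, 2.3 falling to 1.5 (max/min 1.53): 32.2%, still a success. Not every triggered patient flips.
- Reference 2.0, flat at 2.9 to Day 28: 34.9%, success. If creatinine then improves to 1.9 at Day 90 (2.9/1.9 = 1.53), the Day 28 loss becomes 68.3%: failure.

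**7. Link with Exhibit 1.** As worded, two or more values within 2 days of dosing that agree within 25% enter the reference algorithm. Suppose this inflates a non-black man's reference to 3.1 at age 60, with Day 10 creatinine 3.1 and Day 28 creatinine 2.0 (max/min 1.55). The rule resets the reference to 1.071: loss 51.4%, failure. If the rule is dropped alone, the reference stays at 3.1 and he succeeds. If he is flat from Day 10 at 3.1 or 2.0, the rule never fires.

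**8. Planned checks.** SAP 3.10.7 varies only Day 28 creatinine. The medical review in 3.10.1 and 3.10.2 may change baseline AKI stage, but 3.10.2 keeps the algorithm for eGFR.

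**The case against.** **The recorded reference may be wrong.** This is the strongest defence. Exhibit 1 accepts values up to 12 months old, while Protocol 6.2 excludes documented AKI only in the last 30 days. A recorded value above 1.4 could come from an earlier acute episode, and replacing it could be right. This stands: which analysis is primary is partly a trade-off, and cases A to C assume the recorded value is a true pre-illness value.

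**An adjudicated reference is foreseen.** The footnote to Exhibit 2 allows an independently adjudicated reference depending on the analysis, and SAP 3.10.1 and 3.10.2 promise sensitivity analyses as needed. So it would be too strong to say that no alternative reference is contemplated. But the footnote belongs to the AKI staging table, and none of this text clearly reaches the eGFR endpoint.

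**Near-dosing values may not be meant.** Exhibit 1 speaks of historical values before screening, and using screening values as reference would compare them with themselves. A reader might infer that acute values definitely enter the reference. The wording supports only an ambiguity, although several values are likely to exist because Protocol 7.3 records creatinine every 6 hours.

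**The rule is the same in both arms and written in advance.** This is correct. A reader might still infer inflated type I error, since treatment could affect post-randomisation creatinine; the documents do not show it.

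**Conclusion.** The inconsistent baseline is an error as written in the primary endpoint derivation and must be fixed. SAP 1 lets the SAP prevail over the protocol, but that does not help when the SAP disagrees with itself.

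Once loss is measured from reference eGFR, SAP 3.10.6 breaks the ordering by Day 28 function for some patients: 50.1% loss and failure at eGFR 35.4, against 35.7% and success at eGFR 22.8. This rests on reading the trigger as at least 1.5 and 1.4 as mg/dL. Correcting the rule is a should-fix that depends on the baseline being settled. Confidence in the arithmetic is high. Confidence that Exhibit 1 admits near-dosing values is moderate. The fallback mismatch is certain but of lower severity.

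A reader might infer that many patients are misclassified or that power falls by a definite amount. The documents give no distribution of reference values or of creatinine after Day 10, so neither can be computed. Nor is the rule always stricter: for a black man aged 20 with reference 1.41, the replacement of 1.545 is more lenient.

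**What to change.** Before unblinding, and in one SAP revision:

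- **(a) Must fix.** Rewrite the loss formulas in 3.10.3, 3.10.4 and 3.10.5, and the prose in 2.1.1 and 4.1, so that loss is measured from reference eGFR.
- **(b) Should fix, given (a).** Set the primary reference without post-randomisation creatinine: recorded pre-illness values, or the MDRD fallback when there are none. Keep the Day 10 replacement as a sensitivity analysis with a stated inequality and unit, a last day no later than the Day 28 assessment, and counts of replaced references by arm.
- **(c) Should fix, together with (b).** State in Exhibit 1 that values within 2 days of dosing enter only under the protocol's condition that the patient was not acutely ill on admission. Step 7 shows why (b) should not go ahead alone.
- **(d) Lower severity.** Code the fallback as (75 / (175 × age^-0.203 × sex × race))^(-1/1.154), with the forward equation's race factor. At age 60 this gives 1.014 for a non-black man and 0.783 for a non-black woman.

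The cost is SAP wording and derivation code. The downside of (b) is that a recorded reference that is not truly pre-illness stays in the primary analysis; the sensitivity analysis shows how much that matters. Under (c), some more patients may use the fallback, and the documents do not show how many.
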